8.4.1. Unscheduled Visits

If disease activity increases or other concerns arise between regularly scheduled visits, participants should be instructed to contact study personnel and may be asked to return to the study site for an "unscheduled" visit.

Unscheduled visits may be performed for significant food allergy episodes which may be reported by the subject between regularly scheduled visits. Significant food allergy episodes are defined as those for which epinephrine is administered based on criteria in the subject's Food Allergy Action Plan. Unscheduled visits may include physical assessment, blood draw and/or skin prick test. Review of the circumstances around the episode and appropriate documentation of the adverse event will be recorded in the study chart.

Visit Windows

Table 3: Visit Windows

Visit Type	Target Date	Visit Window			
Screening/Baseline/Randomization	Day -300 to 0	Day -300 to 0			
Initial Dose Escalation Day	Day 0	Day 0 (by definition)			
Dose Escalation Phase	Weeks 2, 4, 6, 8 until maintenance				
Dose Escalation Phase	dose is reached]	±14 days			
Maintenance Phase	Weeks 52, 65, 78, 91, and 104				
Telerance Dhace	Weeks 117 (or equivalent), 130, 143,				
	and 156				

9. Mechanistic Assays

Comparisons for each of the parameters discussed below could occur between:

- Treatment vs. Placebo group, and
- On Treatment vs. Baseline for each subject, and
- Tolerant vs. Desensitized vs. Refractory (those that terminate early due to not being able to be desensitized) clinical outcomes

I) Serum Assays

Table 4: Serum Assays

Panel	Volume needed for each sample collection
Specific IgE, IgG4, IgA anti-peanut and the component-resolved (presume IgE and IgG4 anti-Ara h 1,2,3,6,8)	1 ml
Epitope Array Peanut	350 microliters

Table 5: Expected Results for Serum Parameters

Parameter	On Therapy	Tolerance	Desensitization	Refractory
Specific IgE And Specific IgG4	Progressive decrease in specific IgE to peanut and increase in specific IgG4	Low specific IgE and increased IgG4 which persists despite the 3 month period of abstinence	Low specific IgE and increased IgG4 which reverses in the 3 month period of abstinence	No change in specific IgG4 to peanut
Epitope Array for IgE for peanut	Progressive Inhibitory antibodies	Lowest epitope spreading at	Intermediate epitope spreading at	Highest epitope spreading at baseline predicts

peptides— predictive marker for outcome	present in epitope array	baseline predicts tolerance	baseline predicts tolerance	refractory outcome
Specific IgA	Progressive increases in specific IgA over time	Increased specific IgA which persists despite the 3 month period of abstinence	Intermediate levels of specific IgA which persists despite the 3 month period of abstinence	No change

Note: Compared to placebo, in which we assume no changes will occur.

II) Cell components for CyTOF Parameters

Table 6: Possible Cell Components for CyTOF Parameters

Panel A Rationale		Panel B	Rationale					
"T" Marker		"Non T" Marker						
CD4	T cell panel for immunoprofiling	CD19	B cell panel for immunoprofiling					
CD8	T cell panel for immunoprofiling	CD20	B cell panel for immunoprofiling					
CD3	T cell panel for immunoprofiling	CD3	B cell panel for immunoprofiling					
LAG3	Marker for Tr1	CD24	Mature B cell marker					
CD45RA	Naïve phenotype	CD27	Memory B cell					
Ki-67	Proliferation marker	CD38	В					
CD40L	Activation marker	CD16	NK marker					
CD69	Activation marker	CD56	NK marker					
HLA-DR	MHC Class II	CD94	NK marker					
PD-1	Programmed-death (Treg subset)	CD314	iNKT					
Helios	Ikaros Family Transcription Factor, preferentially expressed on induced Treg	Lin	DC marker					
Foxp3	Transcription Factor involved in Treg development and function	CD123	DC and basophil marker					
CD127	Marker for native Treg	CD11c	DC marker					
CD49b	Marker for Tr1	CD103	Pro-tolerance DC cell (GI tract?)					
CCR4	Chemokine receptor for T cell trafficking into local tissues	CCR9	Pro-tolerance DC cell					
CCR8	Chemokine receptor for T cell trafficking into local tissues	HLA DR	MHC Class II					
CCR6	Chemokine receptor for T cell trafficking into local tissues	CD63	Basophil activation marker					
IL-17	Th17 cell ICS	CD203c	Basophil activation marker					
IL-5	Th2 cell ICS	Psyk	Basophil activation phosphoepitope					
pSTAT1	Th1 ICS	mTOR	Basophil activation phosphoepitope					

pSTAT3	Th17 ICS	pS6	Basophil activation phosphoepitope
pSTAT5	Treg ICS	TLR9	Innate immune pathway associated with allergy treatment
pSTAT6	Th2 ICS	CD8	T cell, NKT
GATA-3	Directs Th2 development	Ki67	proliferation
T-bet	Directs Th1 development	TSLP	Pro-allergy ICS
IL-10	Treg ICS	OX40L	Allergy modifier
TGF-b	Treg ICS	TSLP receptor	DC marker pro allergy
IFN-g	Th1 ICS		
IL-13	Th2 ICS		
IL-4	Th2 ICS	Live/Dead	
Tetramer Positive	Antigen-specific		
Live/Dead			

Subset Definitions:

- T cells: CD3, CD4, CD8, CD27, CD45RA, CD28, CCR4, CCR8
- Activated T cells: CD3, CD4, CD8, CD38, HLA-DR, PD-1
- NK/NKT cells: CD3, CD8, CD16, CD56, CD94, CD314 (NKG2D), HLA-DR
- B cells: CD3, CD19, CD20, CD24, CD27, CD38,
- Regulatory T cells: CD3, CD4, CD8, CD25, CD127, CD45RA, GITR, Helios, PD-1, Foxp3, CD49b/LAG3
- DC: Lin-, HLA DR+, CCR9, CD103
- Plasmacytoid DC: Lin-, HLA DR+, CD11c-, CD123+
- Myeloid DC: Lin-, HLA DR+, CD11c+, CD123-
- Basophils: HLADR-, CD123+, CD63, CD203c, psyk, mTOR, pS6
- Innate Immunity: TLR9
- Plus Tetramer Positive T cells to be gated

Typical Intracellular Staining:

- Ki-67
- IFNgamma
- IL-4
- IL-5
- IL-9
- IL-13
- IL-10
- TGF-beta
- IL-17
- pSTAT-1
- PSTAT-3
- pSTAT-5
- pSTAT-6
- Helios
- Foxp3
- GATA-3
- Tbet
- Psyk
- pS6
- mTOR

Table 7: Expected Results for Cell Parameters

Parameter	On Therapy	Tolerance	Desensitization	Refractory
Th2	Progressive Low Th2 cell decrease in Th2 numbers and absolute numbers decreased ability and ICS to proliferate in transcription response to peanut factors and Th2 which persists		Low Th2 cells and low ability to proliferate in response to peanut which does not persist	No change (compared to placebo or to baseline)
	cytokines	despite the 3 month period of abstinence	within the 3 month period of abstinence	
Th1	Progressive increase in Th1 absolute numbers and ICS transcription factors and Th1 cytokines	HighTh1 cell numbers and increased ability to proliferate in response to peanut which persists despite the 3 month period of abstinence	High Th1 cell numbers and ability to proliferate in response to peanut which does not persist within the 3 month period of abstinence	No change (ibid)
Th17	Do not expect change	Do not expect change	Do not expect change	Do not expect change (ibid)
Treg	Progressive increase in absolute counts of Treg but then decline by 12 mo.	High Treg cell numbers and decreased ability to proliferate in response to peanut which persists despite the 3 month period of abstinence	Intermediate Treg cell numbers and decreased ability to proliferate in response to peanut which does not persist within the 3 month period of abstinence	No change (ibid)
NKT	Progressive increase in absolute counts of NKT cells	High NKT cell numbers associated with tolerance	Intermediate NKT cell numbers associated with desensitization	No change (ibid)
DC	Progressive decrease of TSLP receptor in mDCs, progressive increase in CD103 and CCR9 in DCs	Low TSLP receptor expression in mDCs, High DC expression of CD103 and CCR9	Intermediate TSLP receptor expression in mDCs and intermediate DC expression of CD103 and CCR9	No change (ibid)
Cell death markers	Progressive increase in cell death of allergen-	Highest cell death of allergen-specific Th2 memory cells	Intermediate cell death of allergen-specific	No change (ibid)

	specific Th2 memory cells		Th2 memory cells	
Chemokine receptors	Progressive increase in CCR4 and CCR8 in Treg	Highest expression of CCR4 and CCR8 in Treg	Intermediate expression of CCR4 and CCR8 in Treg	No change (ibid)
Allergen specific cells	Switch from mostly Th2 to Th1 or Treg subset over course of therapy	Lack of Th2 cytokines and transc. factors in gated tetramer positive population (i.e. no pSTAT6, no IL-4, no IL-13, no IL-5, no GATA-3 expression upon peanut stimulation)	Intermediate decrease in Th2 cytokines and transc. factors in gated tetramer positive population	No change (ibid)

Note: Compared to placebo, in which we assume no changes will occur.

III) Sample Basophil Assay:

Table 8: Expected Results for Basophil Activation Parameters

Parameter	On Therapy	Tolerance	Desensitization	Refractory
CD203c/CD63	During course of therapy, will see decrease in basophil reactivity sooner than lowering of specific IgE	Lack of basophil reactivity to peanut stimulation persists after 3 mo abstinence	Basophil reactivity returns during the 3 mo abstinence.	No change in basophil reactivity (ibid)

Logistics: Blood samples will be collected every 12-13 weeks during the subject's participation in the study. Volumes collected will follow NIH guidelines (for children: 5 ml/kg at any single draw, no more than 9.5 ml/kg over an 8-week period; adults: the smaller of 10.5 ml/kg or 550 ml total at any single draw).

IV) GI biopsy assays:

We will perform three major procedures on the GI biopsies:

- a. immunohistochemistry to identify cells-inflammatory and regulatory (mast cells, basophils, eosinophils, T cells, B cells, dendritic cells, and epithelial cells and associated markers –for example TSLP, IL-33, IL-18, IL-10, CD103, IL-4, IL-13, histamine, STAT6, GATA3, T-bet, IFN-g, TGF-b)
- b. single cell sorting with RNA Seq
- c. cryopreservation for future analysis outside the scope of the proposal

10.Biospecimen Storage

Biospecimen storage will occur in the [name] laboratory using a previously validated and published storage procedure for samples (available upon request).

11.Criteria for Participant and Study Completion and Premature Study Termination

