7.4. Rescue Medications

Treatment of individual allergic reactions during peanut OIT therapy should be with either an antihistamine and/or epinephrine, along with IV fluids, albuterol and steroids as indicated. Subjects and parents are likely to already have EpiPens[®], but for those who do not, a prescription for EpiPens[®] (or equivalent device) will be provided. Subjects and parents will be trained in proper use and will be able to demonstrate proper technique with the EpiPen[®] (or equivalent device).

Generally, for mild and moderate symptoms, the subject should receive antihistamines, and for more severe symptoms, the subjects should receive epinephrine, antihistamines, and then the other medications as indicated. If severe anaphylaxis occurs at any time, dose escalation will stop and the dose will be reduced to the last tolerated dose and the subject continued on that dose as long-term maintenance without further escalation.

Antihistamines

If a subject requires only antihistamines for treatment of allergic symptoms, the dose escalation can be continued. If symptoms during a build-up day require antihistamines in multiple doses or in combination with other medications (except epinephrine), there should be a dose reduction by 1-2 doses with the next dose given in CFRU. If dose escalation fails or requires treatment after two more escalation attempts each spaced 2 to 4 weeks apart, the dose should be reduced to the last tolerated dose and continued long term without further escalation.

Epinephrine

Any reaction (in CFRU or at home) that requires two or more doses of epinephrine will halt further dose escalation for this individual. Maintenance on the last tolerated dose would be continued.

CFRU

If a single administration of epinephrine is required during in CFRU escalation, the dose should be reduced by two doses, and the subject continued on that dose for four weeks. After 4 weeks at the reduced dose, an escalation attempt may be tried in CFRU.

If a single administration of epinephrine is required a second consecutive time during this escalation attempt, the dose should be reduced by two doses, and the subject continues on that dose for 6-8 weeks. After 6-8 weeks at the reduced dose, an escalation attempt may be tried in CFRU.

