After subjects have met the criteria outlined above (Section 3.1), medical history, diet history, spirometry, SPT, and a physical assessment will be performed. These subjects will be randomized 1:1 either to avoid OIT therapy (**see Figure 1**), and begin the avoidance phase, or they will be randomized to decrease their daily dose to 300 mg of peanut protein. After 3 months both arms will be re-challenged with 4,000 mg peanut protein, and then every 13 weeks for up to 4 additional OFCs. The placebo group may be unblinded to the research staff at week 117.

Peanut OIT:

Initial Dose Escalation Day (Day 0) – The Initial Dose Escalation (IDE) Day will be done at the CFRU and consist of peanut OIT dosing, beginning at 0.5 mg of peanut protein with graduated doses every 30 minutes up to 6 mg (see schedule for initial day dose escalation, **Table 1**). Subjects will not have active wheezing, spirometry demonstrating FEV1 <80% predicted, or a current flare of atopic dermatitis that contraindicates dosing in the clinical judgment of the study physician. A physician will be present at all times during any of the CFRU peanut OIT dosing visits and will be available to respond within 60 seconds to any allergic reaction. Subjects tolerating the 6 mg single dose will remain on that daily dose for 2 weeks. They will then return every 2 weeks to the CFRU for single updose. Subjects who do not tolerate the 1.5 mg dose will be considered treatment failures and will not initiate home dosing.

Table 1: Peanut Protein or Placebo (oat protein)Dosage Escalation Schedule on the Initial Dose Escalation Day

Dose #	Peanut Dose	Cumulative Peanut Dose	
1	0.5 mg	0.5 mg	
2	0.8 mg	1.3 mg	
3	1.5 mg	2.8 mg	
4	3.0 mg	5.8 mg	

5 6.0 mg 11.8 mg

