Up-dosing phase (build-up phase) (Week 1-44): Subjects will receive subsequent doses (**Table 2**) at home for the next 14 days. Subjects who tolerate only 1.5 mg on the IDED will return in 7 days for updosing to 3 mg and then return 7 days later for updosing to 6 mg before proceeding to dose #6. Subjects who tolerate only 3 mg on the IDED will return in 7 days for updosing to 6 mg before proceeding to dose #6. Subjects will be instructed to continue dietary peanut avoidance throughout the entire study. They will also be instructed not to introduce any new foods to the diet and to continue avoidance of the subject's other known food allergens, if any. At 2-week intervals, the subjects will return for a possible increase in the daily oral dose until they reach 4,000 mg peanut protein build-up phase).

During dose escalation, there should be increased hydration (i.e. about 16 oz or more given orally) and restricted exercise for 2 hours after dosing.

Dose #	Dose	Interval (Weeks)	% of Increase
5	6 mg	2	Initial Dose Escalation Day
6	12 mg	2	100%
7	25 mg	2	108%
8	50 mg	2	100%
9	75 mg	2	50%
10	100 mg	2	33%
11	125 mg	2	25%
12	156 mg	2	25%
13	195 mg	2	25%
14	245 mg	2	25%
15	306 mg	2	25%
16	383 mg	2	25%
17	479 mg	2	25%
18	599 mg	2	25%
19	749 mg	2	25%
20	936 mg	2	25%
21	1,170 mg	2	25%
22	1,463 mg	2	25%
23	1,829 mg	2	25%
24	2,286 mg	2	25%
25	2,858 mg	2	25%
26	3,573 mg	2	25%
27	4,000 mg	2	12%

Table 2: Dail	y Peanut Protein	Dosing and Increas	se Schedule for	Build-Up Phase
---------------	------------------	---------------------------	-----------------	----------------

Subjects will begin the CFRU dosing schedule as outlined above until 4,000 mg of peanut protein is reached. Any updosing attempts may be postponed for 1-2 extra visits based on clinical judgment. However, an updosing attempt must be made within a maximum of 3 consecutive scheduled clinic visits. Subjects should withhold their daily home dose and any prophylactic antihistamines on the in-CFRU updosing day but should take all other prescribed medications. Note that the daily home dose should be taken as part of a meal at a consistent time (within 24±2 hours of the previous day's dose), and it is critical to take the dose every day. Doses should be separated by at least 12 hours. Subjects who require dosing reduction during the 2-week period due to illness will undergo an attempted updosing only after resuming their full dose for a minimum 3 days.

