Appendix 1: Schedule of Events

*Initial Dose Escalation Day

Informed consent obtained prior to completion of any study procedures ^Subjects return for up-dosing every 2 weeks. Blood to be obtained every 12 weeks *Urine pregnancy test to be performed preferentially. Serum pregnancy test to be performed to confirm positive urine results, if any.

****Week number may be + or -2 weeks.

Study Stage		Buil	d-up F	hase	(Weeł	(#)				Main	tenan	ce Pha	ise						Early Completion
Time	Week****	30	32	34	36	38	40	42	44	52	65	78	91	104	117	130	143	156	Withdrawal/
															^				Early Termination
	Visit #	15	16	17	18	19	20	21	22	23	24	25	26	27	28	29	30	31	
Informed Consent*	**																		
Medical History																			
Physical Exam		Х	Х	Х	Х	Х	Х	Х	Х	Х	Х	Х	Х	Х	Х	Х	Х	Х	X
Concomitant Medi	ications	Х	Х	Х	Х	Х	Х	Х	Х	Х	Х	Х	Х	Х	Х	Х	Х	Х	Х
Adverse Events		Х	Х	Х	Х	Х	Х	Х	Х	Х	Х	Х	Х	Х	Х	Х	Х	Х	X
Peanut/Placebo Do	osing	Х	Х	Х	Х	Х	Х	Х	Х										
Total IgE										Х	Х	Х	Х	Х	Х	Х	Х	Х	Х
Peanut Specific IgE	and IgG4									Х	Х	Х	Х	Х	Х	Х	Х	Х	Х
Peanut skin testing	5									Х	Х	Х	Х	Х	Х	Х	Х	Х	X
CBC with differenti	ial									Х	Х	Х	Х	Х	Х	Х	Х	Х	Х
Mechanistic labs					Х					Х	Х	Х	Х	Х	Х	Х	Х	Х	Х
Serum or urine pre	egnancy***									Х		Х		Х		Х		Х	
Spirometry		Х	Х	Х	Х	Х	Х	Х	Х	Х	Х	Х	Х	Х	Х	Х	Х	Х	X
Screening DBPCFC																			
On-Study DBPCFC ⁺														Х	Х	Х	Х	Х	
Diaries		Х	Х	Х	Х	Х	Х	Х	Х	Х	Х	Х	Х	Х	Х	Х	Х	Х	Х
EpiPen [®] Training																			

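### The ±14-day build-up visit window is as wide as the 14-day updosing interval, so a dose increase can be in window after only a few days on the current dose, against the two weeks per dose set elsewhere

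*Protocol*

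**What the plan says.** Table 3 in the Protocol, under Section 8.4.1, lists the dose-escalation visits as "Weeks 2, 4, 6, 8 until maintenance" dose is reached, with a window of ±14 days. The Appendix 1 schedule carries a matching footnote: "Week number may be + or -2 weeks". Appendix 1 also marks study-product dosing at every build-up visit, so a window on the visit is in practice a window on the increase.

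The dosing text fixes the time on each dose. Section 8.3 says of the first home dose: "Subjects tolerating the 6 mg single dose will remain on that daily dose for 2 weeks", followed by "They will then return every 2 weeks to the CFRU for single updose". It repeats the rule for the rest of build-up: "At 2-week intervals, the subjects will return for a possible increase in the daily oral dose until they reach 4,000 mg". Table 2 gives an interval of 2 weeks for every step. Section 6.4 puts the next increase two weeks after a symptom-free one.

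The stated exceptions are these:
- **Shorter steps** after a partial initial escalation day, for example "Subjects who tolerate only 3 mg on the IDED will return in 7 days for updosing to 6 mg before proceeding to dose #6"; the 1.5 mg step is handled the same way.
- **Illness reductions**, where Section 8.3 asks for at least 3 days back on the full dose before an increase.
- **Longer intervals**: "Any updosing attempts may be postponed for 1-2 extra visits based on clinical judgment" in Section 8.3, and holds after epinephrine in Section 7.4, the first of which reads "the dose should be reduced by two doses, and the subject continued on that dose for four weeks".

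No section says whether the visit window or the dosing interval prevails when they disagree.

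**The concern.** A visit window is normally read as the tolerance on the scheduled interval. Here the tolerance equals the interval, so a scheduler or monitor working from Table 3 or the footnote would pass an increase made a few days after the previous one, while Section 15.1 would class the same increase as a deviation. One visit passes one rule and breaks another.

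What is at stake is the conduct of build-up. Section 5.4 names anaphylaxis as a risk of updosing. The increase itself is supervised, but the new dose is then taken daily at home. Section 1.2 rests its claim of tolerability on a regimen with increases every two weeks; shorter steps fall outside what that claim covers. The late half of the window has an evident use, because illness, postponement and holds all lengthen time on dose. The early half has no stated purpose.

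**Working it through.** **Inputs.** Visit spacing 14 days (Table 3, Table 2, Section 8.3). Window w = 14 days (Table 3; 2 weeks in the Appendix 1 footnote). Initial escalation day = Day 0 (Table 3). Doses #5 = 6 mg, #6 = 12 mg, #7 = 25 mg, #27 = 4,000 mg (Table 2).

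**The protocol's own figure.** From dose #5 to dose #27 there are 27 − 5 = 22 increases. At 2 weeks each, 22 × 2 = 44 weeks, which matches the Week 44 end of build-up in Section 8.3. The timetable therefore assumes a full two weeks on every dose.

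**Targets fixed from Day 0.**
- Week 2: 14 ± 14 = Days 0 to 28.
- Week 4: 28 ± 14 = Days 14 to 42.
- Minimum gap = max(0, 14 − 2w) = max(0, 14 − 28) = 0 days.

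**Targets counted from the previous visit.**
- Minimum gap = max(0, 14 − w) = 14 − 14 = 0 days.

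**Example.**
- Week 2 visit on Day 24 (target + 10): in window, 12 mg started.
- Week 4 visit on Day 28 (target + 0): in window, 25 mg started, listed in Table 2 as a 108% increase.
- Time on 12 mg = 28 − 24 = 4 days, which is 14 − 4 = 10 days short.
- Counted from the previous visit, the target is 24 + 14 = Day 38 and the window is Days 24 to 52, so Day 28 is again in window.

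**How far it reaches.** With targets fixed from Day 0, no visit can fall more than 14 days ahead of schedule. The Week 44 visit (Day 308) can come no earlier than Day 294, or Week 42. In the example the subject spent 24 days on 6 mg and 4 on 12 mg, 28 in all, which is the nominal time for two doses.

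**Would a narrower symmetric window do?** As an illustration:

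| Window | Minimum gap, from Day 0 | Minimum gap, from previous visit |
|---|---|---|
| ±14 days | 0 days | 0 days |
| ±7 days | 0 days | 7 days |
| ±3 days | 8 days | 11 days |
| ±2 days | 10 days | 12 days |

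Any early side leaves less than 14 days.

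**The case against.** The strongest reply is that these are two cumulative rules. Table 3 governs attendance and grants no dose increase; the condition for an increase is stated repeatedly in Sections 6.4 and 8.3 and in Table 2. Both can be met: a subject seen on Day 24 can return on Day 38, which is 14 days later and inside the Week 4 window of Days 14 to 42. This stands, and it is why the point is an inconsistency and not a permission. It does not remove the point, because no text says that the interval limits the window.

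It is also fair that 14 days is not universal (7-day steps, and the 3-day rule after illness), that each increase is preceded by an eligibility check, and that time on dose does not appear in the list of safety considerations in Section 3.1. Table 3 is damaged in the extracted text and the ±14 days may be one cell shared by several rows. It would still cover build-up, and the footnote confirms it independently.

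Three stronger readings are tempting and unsupported. A reader might infer that same-day or back-to-back increases are allowed; Section 8.3 provides for a single increase per visit and at least 12 hours between doses, and an early increase departs from the dosing text. A reader might infer that the whole build-up can be compressed; on the Day 0 count it can gain at most two weeks. A reader might infer demonstrated harm or a distorted efficacy result; the document has no data on shorter intervals, and nothing here bears on the primary or secondary efficacy endpoints.

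**Conclusion.** The inconsistency is real. The window alone puts the minimum time on a dose at 0 days against a stated 14, and an ordinary sequence, a late visit followed by a return to the calendar, gives 4 days. The zero minimum holds whether targets run from Day 0 or from the previous visit. The statement that the effect is local rests on targets being fixed from Day 0, as the week numbers in Table 3 imply.

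The size is modest. The dosing text already makes an early increase a deviation, and both rules can be satisfied together. It is worth correcting because it concerns the pace of allergen dosing, nothing in the document justifies the early 14 days, and the correction is cheap.

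**What to change.** Change the build-up row of Table 3 and the Appendix 1 footnote as follows:

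1. Make the build-up window late-sided only. It opens when the required interval is complete and closes 14 days later.
2. Count the interval from the start of the current dose level, whether that level was reached by an increase or a reduction.
3. State that no increase may occur before the interval required by Table 2 or Sections 6.4, 7.4 and 8.3 is complete: 14 days by default, 7 days for the 1.5 mg and 3 mg steps after the initial escalation day, and 4 or 6–8 weeks after epinephrine as Section 7.4 sets out. Keep the 3-day rule after an illness reduction and the permitted postponements as they are.
4. If the clinical team wants some early tolerance, write it as one explicit minimum number of days on dose, in place of the 14, so that the text does not forbid early increases and allow them at once.

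In the example, a visit on Day 24 would then open the next window on Day 38 and close it on Day 52.

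The cost is amendment wording for one row and one footnote. Sites lose a little flexibility for early visits, and days lost to a late visit cannot be regained. There is room for this: maintenance must be reached 13 weeks before Week 104, that is by Week 91, against an expected 44 to 78 weeks, leaving 13 to 47 weeks.
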